COVER SHEET FOR THERAPEUTIC EFFICACY TEST PROTOCOL

Title	Monitoring and evaluation of the efficacy and safety of Artesunate-Mefloquine (ASMQ) and Artesunate-Pyronaridine (ASP) for the treatment of uncomplicated Plasmodium falciparum and Plasmodium vivax malaria in Cambodia
Study sites	
Site 1: Trapeang Cho Health Center, Kampong Speu district, Kampong Speu province ACT tested: Artesunate-Mefloquine (ASMQ)
 
Site 2: Veunsai Health Center, Veunsai district, Rattanakiri province ACT tested: Artesunate-Pyronaridine (Pyramax)
 
Site 3: Chambak Health Center, Phnom Sruoch district, Kampong Speu province ACT tested: Artesunate-Mefloquine (ASMQ)
 
Site 4: Cheu Tom Health Center, Krakor district, Pursat province ACT tested: Artesunate-Pyronaridine (Pyramax)
 
Site 5: Keo Seima Health Center, Saen Monourom district, Mondulkiri ACT tested: Artesunate-Mefloquine (ASMQ)

Protocol submission date	10/03/2020
Protocol number	Cambodia 1
Principal investigator	
[name]. MD, DrPH., Postdoc National Centre for Parasitology, Entomology and Malaria Control Program, Cambodia Head of Health Research Unit [contact] [contact] Email: [contact]

Co- investigator	
[name]., MD., DrPHS Vice Director National Centre for Parasitology, Entomology and Malaria Control Cambodia [name] [contact] E-mail: [contact]

Co-investigator	
[name] [name], M.D., MTM Malaria Medical Officer World Health Organization [contact] [contact]

Co-investigator	
[name] [name] Antimalarial drug resistance Global malaria Programme World Health Organization [name] [contact] [contact] Email: [contact]

Participating institutions	Institute Pasteur du Cambodge, Phnom Penh [name] [contact] [name]
Study dates	From June to December 2018
Sponsor	Ministry of Health, Cambodia [name] [contact] Office: [name] [contact] [contact] Email: [contact]

SYNOPSIS

Title: Artesunate-Mefloquine (ASMQ) and Artesunate-Pyronaridine (ASP) for the treatment of uncomplicated Plasmodium falciparum and Plasmodium vivax malaria.

Purpose: To assess the efficacy of the current first line treatment policy; To assess the efficacy of a new antimalarial drug to support updating of the national policy.

Study period: June to December 2020

Study Sites:

1- ASMQ: Trapeang Cho, Kampong Speu district, Kampong Speu province; Chambak, Phnom Srouch district, Kampong Speu; Keo Seima, Saen Monourom, Mondulkiri.

2- ASP: Veunsai, Veunsai district, Rattanakiri; Cheu Tom, Krakor district, Pursat

Study Design: This surveillance study is a one arm prospective study

Patient population by treatment regimen:

Artesunate-Mefloquine (ASMQ)

Febrile patients aged between 18 years and 60 years, with confirmed uncomplicated *P. falciparum* and *P. vivax* infections.

Artesunate-Pyronaridine (ASP)

Febrile patients aged between 2 years and 60 years, with confirmed uncomplicated *P. falciparum* and *P. vivax* infections.

Sample Size: 600 (120 in one site: 60 *P. falciparum* cases and 60 patients *P. vivax* cases)

Treatment(s) and follow-up: artesunate-mefloquine (ASMQ) will follow a dosing chart in Annex 3; one tablet of Pyronaridine-Artesunate contains 60mg artesunate+ 180mg pyronaridine; dosing is given based on the weight band (Annex 3). Primaquine will be administered as a single 15-mg adult dose (0.25 mg base/kg).

Clinical and parasitological parameters will be monitored over a 42-day follow-up period to evaluate drug efficacy.

Primary endpoints: The proportion of patients with early treatment failure, late clinical failure, late parasitological failure or an adequate clinical and parasitological response as indicators of efficacy. Recrudescence will be distinguished from re-infection by polymerase chain reaction (PCR) analysis.

Secondary endpoints: The frequency and nature of adverse events

Exploratory endpoints:

- to assess the in vitro susceptibility of *P. falciparum* isolates to dihydroartemisinin, piperaquine, artesunate and mefloquine at D0 and Day of recrudescence;
- to determine the polymorphism of molecular markers of *Plasmodium falciparum* and Kelch gene

1. BACKGROUND

The current first line treatment of both *P. falciparum* and *vivax* malaria infections in Cambodia is artesunate-mefloquine (ASMQ) fixed dose and Quinine and Tetracycline; the patients receive the treatment at all facilities with free of charge.

Emerging resistance to artemisinins and its partner drugs severely threaten the treatment of falciparum malaria in Cambodia. The ACT resistance has growingly spread to other regions in Cambodia in the last five years to other regions of the country— in the North, East, and South of Cambodia; it may undo all the efforts in malaria elimination and potentially spreads to the regional and global levels. DHA-PIP became less effective after introduced as the first line drug in 2008; the efficacy level of DHA-PIP had gradually decreased to as low as 37.5% in Siem Reap and 60% in Stung Treng in 2014. The recommendation from the drug policy meeting suggested there is an urgent need to change DHA-PIP, the first-line treatment between 2007 and 2014, to artesunate-mefloquine (ASMQ).

Sensitized with the previous observation of efficacy of artesunate-mefloquine enduring about 3 or 4 years, the national program in collaboration with WHO is to closely monitor the efficacy and safety of ASMQ even though its efficacious level is high. At the same time, there is a need to explore the alternative ACT before the current ACT becomes less effective. Pyronaridine-artesunate could be an alternative option for the treatment of uncomplicated falciparum malaria in western Cambodia. On 16 February 2012, the European Medicine Agency (according to Article 58) adopted a positive scientific opinion for pyronaridine-artesunate (Pyramax®). Pyronaridine-artesunate was pre-qualified by WHO in adults and children >20 kg in countries with documented artemisinin resistance including Cambodia, where the drug was tested in 2005, 2008 and 2104.

Pyronaridine-artesunate was first used as a fixed combination in 2005 in the context of the Phase II development; it is however not yet commercially available in Cambodia. The TES result in 2017 indicated that ASMQ remained effective in the west part of the country and the potential alternative ACT, artesunate-pyronaridine (ASP), also proved to be highly effective in the north and in the east of the country.

It is necessary to closely monitor the efficacy and safety of ASMQ in the east and the south of and re-evaluate the efficacy of ASP for the treatment of both species (*P. f* and *P. v* malaria) in the west of Cambodia in 2020; the results of this study will be used to assist the Ministry of

Health of Cambodia in assessing the current national treatment guidelines and to update the policy if necessary.

2. OBJECTIVES

The general objective of this study is to assess the efficacy and safety of artesunate-mefloquine (ASMQ) and artesunate-pyronaridine (ASP) with a single 15-mg adult dose (0.25 mg base/kg) for the treatment of uncomplicated *P. falciparum* and *P. vivax* malaria infection.

The primary objectives are:

- **to measure the clinical and parasitological efficacy of ASMQ and ASP for the treatment of uncomplicated *P. falciparum* and *P. vivax* in patients who meet the inclusion criteria, suffering from *P. falciparum* and *P. vivax* by determining the proportion with early treatment failure, late clinical failure, late parasitological failure or an adequate clinical and parasitological response as indicators of efficacy;**
- to differentiate recrudescence from new infection by polymerase chain reaction (PCR) analysis for *P. falciparum* malaria;

The secondary objectives are:

- to evaluate the incidence of adverse events; and
- to formulate recommendations and to enable the Ministry of Health to make informed decisions about whether the current national antimalarial treatment guidelines should be updated.

The optional exploratory objectives are:

- to assess the in vitro susceptibility of *P. falciparum* isolates to name of the antimalarial drug(s);
- to determine the polymorphism of molecular markers for name of the antimalarial drug(s) resistance; and
- to determine the blood concentration of name of the antimalarial drug(s).

3. INVESTIGATIONAL PLAN

3.1 Study design

This surveillance study is a one-arm prospective evaluation of clinical and parasitological responses to directly observed treatment for uncomplicated malaria^{1,2}. People with uncomplicated *P. falciparum* who meet the study inclusion criteria will be enrolled, treated on site with ASMQ and ASP, and monitored for 42 days for *P. falciparum* and 28 days for *P. vivax*. The follow-up will consist of a fixed schedule of check-up visits and corresponding clinical and laboratory examinations. On the basis of the results of these assessments, the patients will be classified as having therapeutic failure (early or late) or an adequate response.

¹ WHO. *Assessment and monitoring of antimalarial drug efficacy for the treatment of uncomplicated falciparum malaria*. Geneva, World Health Organization, 2003 (WHO/RBM/HTM/2003.50) (<http://www.who.int/malaria/resistance>).

² WHO. *Method for surveillance of antimalarial drug efficacy*. Geneva, World Health Organization, 2009 (<http://www.who.int/malaria/resistance>).

The proportion of patients experiencing therapeutic failure during the follow-up period will be used to estimate the efficacy of the study drug(s). PCR analysis will be used to distinguish between a true recrudescence due to treatment failure and episodes of reinfection (only *P. f* patients).

3.2 Study site

Kampong Speu

Oral Health Centre in Oral district, Kampong Speu province is located around 100km far from Capital city, Phnom Penh. The estimated population is 76,000 living in 42 villages and in three operational districts: Kampong Speu, Kong Pisey and Odong. Malaria transmission occurs from May to December with a peak between July and September. Most people are a farmer; the others are hunters, forest workers making charcoal or collecting firewood. *Anopheles Dirus* is predominant and not common for *An. Minimus* and *An. Maculatus*.

Mondulkiri

Mondulkiri border the provinces of Kratié to the west, Stung Treng to the northwest, Ratanakiri to the north and the country of Vietnam to the east and south, it is the most sparsely populated province in the country despite being the largest in land area. The capital is the town of Senmonorom. The population lives off the land, planting rice, fruit trees, and a variety of vegetables. Others grow strawberries, coffee, rubber, and cashew nuts. Kaoh Nheaek is a district located in Mondulkiri Province, in Cambodia. According to the 1998 census of Cambodia, it had a population of 8,919. This year the study will conduce at Kaoh Nheaek

Pursat

Located in the west of the country, Pursat is 188km far from Phnom Penh and from Pursat town to Veal Veng is 125km. The total population in Pursat province is 449,599 in 501 villages, 6 districts and 49 communes. The most people in the area are farmer. People go to their farms “called as Chamka” which is far from villages, especially, in the rainy season to harvest season of vegetables and fruits.

3.3 Study population

The study population will consist of patients with uncomplicated *P. falciparum* or *P. vivax* malaria attending the study health clinic who are aged between 2-60 years for ASP and 18-60 years for ASMQ. All adult patients who are above 18 years, age of majority in this country, will sign an informed consent form for participation. Parents or guardians will give informed consent on behalf of children who have not reached the age of majority. Children aged from 12 years and age of majority will be required to consent for participation by signing an informed assent form.

The criteria of the age range included in this surveillance relies on the pattern of malaria infection and their potential involvement in the surveillance study. Those patients under 2 and over 65 are excluded because they may need additional health service support at the higher level while the surveillance study is based at the health centers.

3.4 Timing and duration of study

The study will be conducted during the malaria transmission season, from June to December,

2018.

3.5 Inclusion criteria

- For those receiving ASP: age between 2 and 60 years
- For those receiving ASMQ: age between 18 and 60 years;
- mono-infection with *P. falciparum* or *P. vivax* by microscopy; *P. falciparum* or *P. vivax* parasitaemia of 500-100,000/ μ l asexual forms;
- presence of axillary ≥ 37.5 °C or history of fever during the past 24 h;
- ability to swallow oral [by mouth] medication;
- ability and willingness to comply with the study protocol for the duration of the study and to comply with the study visit schedule; and
- informed consent from the patient or from a parent or guardian in the case of children aged less than 12 years;
- informed assent from any minor participant aged more than 12 years and less than 60 years; and
- consent for pregnancy testing from female of child-bearing potential and from their parent or guardian if under 18 years.

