3.6 Exclusion criteria

- presence of general danger signs in children aged under 5 years or signs of severe falciparum malaria according to the definitions of WHO (Appendix 1);
- Age less than 2 years old and over 60 for ASP, under 18 and over 60 for ASMQ;
- mixed or mono-infection with another *Plasmodium* species detected by microscopy;
- presence of severe malnutrition (defined as a child whose growth standard is below -3 z-score, has symmetrical oedema involving at least the feet or has a mid-upper arm circumference < 115 mm);
- presence of febrile conditions due to diseases other than malaria (e.g. measles, acute lower respiratory tract infection, severe diarrhea with dehydration) or other known underlying chronic or severe diseases (e.g. cardiac, renal and hepatic diseases, HIV/AIDS);
- regular medication, which may interfere with antimalarial pharmacokinetics;
- history of hypersensitivity reactions or contraindications to any of the medicine(s) being tested or used as alternative treatment(s);
- a positive pregnancy test or breastfeeding;
- unable to or unwilling to take pregnancy test or to use contraception for women of child-bearing age (defined as age > 12 years and sexually active).

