4. TREATMENT

4.1 Antimalarial treatment

ASMQ (Artesunate + Mefloquine co formulated).

The adult dose tablet contains 100mg Artesunate plus 220mg Mefloquine and the paediatric tablet contain 55mg Artesunate plus 55 mg Mefloquine. (Refer to Annex table for more detailed dosage).

ASP (Artesunate + Pyronaridine/ Pyramax): Adults and children \geq 20 kg (Refer to Annex table for more detailed dosage).

All doses of medicine will be administered under the supervision of a qualified member of the staff designated by the principal investigator. The study patients will be observed for 30 min after medicine administration for adverse reactions or vomiting. Any patient who vomits during this observation period will be re-treated with the same dose of medicine and observed for an additional 30 min. If the patient vomits again, he or she will be withdrawn and offered rescue therapy. The patients are recommended to stay at the health facility until they complete the treatment course for malaria infection.

All doses of medicine will be administered under the supervision of a qualified member of the staff designated by the principal investigator. The study patients will be observed for 30 min after medicine administration for adverse reactions or vomiting. Any patient who vomits during this observation period will be re-treated with the same dose of medicine and observed for an additional 30 min. If the patient vomits again, he or she will be withdrawn and offered rescue therapy. The patients are recommended to stay at the health facility until they complete the treatment course for malaria infection.

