5.2.2 Body weight

Body weight will be recorded on day 0 to the nearest kilogram on a Salter scale or on a hanging scale for young children. The scales will be properly calibrated. Patients should not wear excessive clothing while being weighed as this can overestimate their true weight. All young children should only wear undergarments while being weighed. The screening weight will be used to satisfy the inclusion or exclusion for nutrition status as well as to calculate the dose (number of tablets) to be administered. When assessing weight-for-height, children over 24 months of age should have their heights measured while standing. For simplicity, however, infants and children under 87 cm can be measured lying down (or supine) and those above 87 cm standing.

The reliability of the scales will be verified before the study begins and checked at regular intervals.

The circumference of the left mid-upper arm will be measured, at the mid-point between the elbow and the shoulder, and will be recorded to the nearest 0.2 cm. Oedema will be assessed by thumb pressure for 3 s on the dorsal surface of both feet.

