9.4 Health-care services

Free health care throughout follow-up for any illness related to malaria will be provided to the study patients regardless of treatment outcome; this includes any expenses related to hospital admission and to adverse medicine reactions, if required.

When prospective or actual participants are found to have diseases unrelated to malaria, the principal investigator should advise them to obtain, or refer them for, medical care.

Any person who decides not to participate or who cannot be enrolled into the study because he or she does not meet the criteria will be referred to the health facility staff. Such people will be treated with antimalarials recommended in the first line treatment in the national treatment guideline and followed-up according to the standard of care established by the Ministry of Health. The principal investigator will ensure that this antimalarial drug is available at the health center.

If a patient is withdrawn from the study before he or she has completed the full course of the treatment, the physician must make all necessary arrangements to provide the patient with the full dose of the medicine being tested or with a full course of antimalarials—ASMQ or ASP (Annex 3) based on the areas where the study site is—recommended in the national treatment guideline.

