APPENDIX 5. CASE SCREENING FORM

Case screening form	
Health centre name:	Study number:
Locality:	Patient screening number:
District:	Date of visit (dd-mm-yyyy):
Province:	
Demographic data	
Date of birth (dd-mm-yyyy):	or estimated age: in:  months or  years
Height (cm):	Weight (kg):
Sex:  Male  Female	
If female, is the patient pregnant?  Yes  No  Not sure (If yes, patient is not eligible)	
If pregnant, provide the date of the last menstrual period (dd-mm-yyyy):	
Pre-treatment temperature	
History of fever in previous 24 h?  Yes  No	
Temperature: °C  Axillary	
Thick and thin blood smears for estimation of P. falciparum parasite counts	
Species:  P. falciparum  P. vivax  P. ovale  P. malariae	
Were species other than P. falciparum present?  Yes  No (If yes, patient is not eligible).	
Approximate number of P. falciparum asexual parasites:	
Presence of 1–200 parasites / 12 white blood cells?  Yes  No (If no, patient is not eligible)	
Presence of P. falciparum gametocytes?  Yes  No	
Has a blood sample for PCR been collected?  Yes  No	
Haematocrit: %	
Urinary analysis (pregnancy test for female patients)	
Result of pregnancy test:  Positive  Negative (If positive, patient is not eligible)	
Inclusion criteria	

 • age between 2 and 60 years • mono-infection with P. falciparum confirmed by positive blood smear (i.e. no mixed infection) • parasitaemia between 500 and 100,000/μl of asexual forms • measured temperature (depending on method of measurement) or history of fever within previous 24 h • ability to swallow medication 	

 • ability and willingness to comply with the study protocol for the duration of the study and to comply with the study visit schedule • absence of severe malnutrition (defined as per protocol) 	

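### ASP eligibility is set by age alone (2 to 60 years), but the protocol gives no ASP dose below 20 kg

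*Protocol*

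**What the plan says.** **Eligibility.** Every ASP eligibility statement is by age, with no weight term:

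- Synopsis, patient population: "Febrile patients aged between 2 years and 60 years".
- Section 3.3: the same range of 2 to 60 years for ASP.
- Section 3.5: "For those receiving ASP: age between 2 and 60 years".
- Section 3.6, as an exclusion: "Age less than 2 years old and over 60 for ASP, under 18 and over 60 for ASMQ".
- Appendix 5, screening form: "age between 2 and 60 years". The form has a field for weight but no eligibility question on it.

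**Treatment.** Section 4.1 describes ASP as for adults and children of at least "20 kg (Refer to Annex table for more detailed dosage"). The table it points to is Appendix 3, Table 1, which doses by body weight. Its first row is 20 to under 24 kg, one tablet, and it lists a single tablet strength (60 mg artesunate, 180 mg pyronaridine). The Background has a similar limit: "Pyronaridine-artesunate was pre-qualified by WHO in adults and children >20 kg".

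**Use of weight.** Section 5.2.2: "The screening weight will be used to satisfy the inclusion or exclusion for nutrition status as well as to calculate the dose".

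**Referral.** Section 9.4 provides that a person who declines, or who "does not meet the criteria will be referred to the health facility staff", is treated under the national guideline.

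**The concern.** The eligibility text and the treatment text describe different ASP populations. One is everyone aged 2 to 60; the other is the part of that group weighing at least 20 kg. The second limit appears only where the drug is described and dosed, not where patients are accepted or refused.

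Two things are at stake. The first is paediatric safety: staff who apply the criteria exactly can consent and enrol a small child, then find no row in the dosing table. They must improvise a dose or turn away a child whom the criteria accept. The second is the description of the population. If sites apply the 20 kg limit informally, the report would give an age range of 2 to 60 years when the youngest part of it was largely not treated, and sites might handle such children differently.

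**Working it through.** **Step 1. Does any eligibility step apply the 20 kg floor?**

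| Place in protocol | Would it stop a well-nourished child aged 2 or over weighing under 20 kg? |
|---|---|
| Synopsis, 3.3, 3.5, 3.6, Appendix 5 | No. Age only. |
| 3.6, severe malnutrition | No. It concerns growth z-score, oedema and arm circumference, so a normally grown small child passes. |
| 3.6, contraindications to the study medicines | Not named. Low weight is not listed as a contraindication. |
| 5.2.2 | No. Screening weight bears on eligibility only through nutrition status; its other use is the tablet count. |
| 6.1, screening steps | No minimum weight. |
| 3.8, erroneous inclusion | No. It covers patients who fail the inclusion criteria. |
| 9.4, referral | No. It covers patients who decline or fail the criteria. |

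No step applies the floor.

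**Step 2. Reproduce the dosing table.** With 180 mg pyronaridine and 60 mg artesunate per tablet, 1, 2, 3 and 4 tablets give 180/60, 360/120, 540/180 and 720/240 mg, as printed. Dose per kg is the daily dose divided by body weight at the two edges of each band (the upper edge is approached, not reached):

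| Band | Pyronaridine, mg/kg/day | Artesunate, mg/kg/day |
|---|---|---|
| 20 to <24 kg | 180/20 = 9.0 to 180/24 = 7.5 | 3.0 to 2.5 |
| 24 to <45 kg | 360/24 = 15.0 to 360/45 = 8.0 | 5.0 to 2.7 |
| 45 to <65 kg | 540/45 = 12.0 to 540/65 = 8.3 | 4.0 to 2.8 |
| 65 kg and above | 720/65 = 11.1, falling with weight | 3.7, falling with weight |

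The bounded bands span 7.5 to 15.0 mg/kg pyronaridine and 2.5 to 5.0 mg/kg artesunate. The maximum is at 24 kg.

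**Step 3. Could the first row be extended downwards?** One tablet at illustrative weights (assumed; the protocol gives no weight distribution):

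| Weight | Pyronaridine, mg/kg | Artesunate, mg/kg | Against the table's maximum |
|---|---|---|---|
| 19.9 kg | 180/19.9 = 9.0 | 60/19.9 = 3.0 | within |
| 16 kg | 180/16 = 11.25 | 60/16 = 3.75 | within |
| 12 kg | 180/12 = 15.0 | 60/12 = 5.0 | equal |
| 10 kg | 180/10 = 18.0 | 60/10 = 6.0 | 20% above (18.0/15.0 = 1.2) |

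One whole tablet stays inside the table's own range from 12 kg to just under 20 kg and exceeds it below 12 kg. No single rule follows from the table, so a dosing decision is missing.

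**Step 4. Effect on the statistics.** Section 8.1 uses a 10% failure rate, 8% precision and 95% confidence: 1.96² × 0.10 × 0.90 / 0.08² ≈ 54.0, raised to 60 per species and site (54/0.9 = 60). Weight does not enter, so the target is unchanged.

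**The case against.** An age range and a weight floor can both apply. Section 4.1 is operative text, so the fault may be only that its limit was not repeated in the criteria. The synopsis ties ASP dosing to weight bands, and Appendix 6 places weighing in the screening block, ahead of the first dose. Staff who look up a child of 15 kg will find no row, and section 4.1 tells them the drug is for 20 kg and above. The likely result is a query or non-enrolment, not a wrong dose. A site might also rely on the contraindication exclusion and refer the child under 9.4. The screening form is generic (it does not carry the ASMQ age range either), so it does not show an intention to enrol small children. Finally, nobody is told to give one tablet below 20 kg, and the protocol states no mg/kg limit for ASP.

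Much of this stands. The risk is lower than the criteria alone suggest, and the mg/kg figures describe a hypothetical departure from the table, not a harm. But the gap stays open. A limit absent from the criteria and the screening form is not an eligibility rule, low weight is not a named contraindication, and the referral route is written for patients who fail criteria that this child meets. Section 6.2 has patients who meet all criteria and have consented go on to treatment.

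**Conclusion.** The concern holds. As written, the ASP criteria admit children for whom the protocol authorises no dose, and the 20 kg limit in section 4.1 and Appendix 3 is enforced at no eligibility step.

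Its extent is limited. It touches only patients under 20 kg at the two ASP sites (Veunsai and Cheu Tom), since ASMQ is restricted to adults. The number could be small or zero, as the protocol gives no age or weight distribution. The one outside assumption is that some children aged 2 or over weigh less than 20 kg, which is a safe one. Harm is not demonstrated, and sample size, endpoints and analysis stay as they are. It should still be corrected, because it concerns paediatric dosing and the definition of the treated population.

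**What to change.** - Add a body weight of at least 20 kg to the ASP population in the synopsis and sections 3.3 and 3.5.
- Add an ASP exclusion for body weight below 20 kg to section 3.6.
- Add a yes/no item on the ASP weight limit to the Appendix 5 screening form, next to the weight it already records.
- Children below the limit then fail a stated criterion, and the referral route in section 9.4 applies to them without further change.
- In the report, describe the ASP population as aged 2 to 60 years and weighing at least 20 kg.

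If the sponsor does intend to treat smaller children with ASP, the alternative is to add a suitable formulation and dose bands below 20 kg to Appendix 3 and to amend section 4.1 to match.

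The first option costs only wording in the protocol and one form, with no new measurement. Its drawback is a slightly narrower eligible population at the two ASP sites.

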9.2 Informed consent

Patients will be included in the study only if they (if adults included) or parents or guardians of children give informed consent. The consent request is available in English and translated into Khmer, will be read entirely to the patient, parent or guardian. Details about the study and its benefits and potential risks will be explained. Once any questions have been answered, a signature will be requested on the document (Appendix 10). If the patient is illiterate, a literate witness must sign; if possible, the signatory will be selected by the prospective participant and will have no connection to the research team. The principal investigator must also obtain and document the assent of children over the age of 12 years and 18 years, but their assent should be accompanied by the consent of a parent or guardian. A child aged between 12 and 18 years who does not agree to participate will not be enrolled in the study and will be referred the health facility staff to be treated according to the standard of care established by the Ministry of Health. Written consent statement for the pregnancy test and the need for contraception is also required for female participants of child-bearing age who are sexually active.

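### Section 3.5 limits parental consent to children under 12, contradicting sections 3.3, 6.1 and 9.2; the contradiction matters for 12- to 17-year-olds at the two ASP sites

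*Protocol*

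**What the plan says.** Two bullets in Protocol section 3.5 govern consent to take part. The first asks for "informed consent from the patient or from a parent or guardian in the case of children aged less than 12 years". The second asks for "informed assent from any minor participant aged more than 12 years and less than 60 years". A third bullet, on pregnancy testing only, brings in the parent or guardian for girls under 18.

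Section 3.3 draws the line at majority. For adults it says: "All adult patients who are above 18 years, age of majority in this country, will sign an informed consent form for participation". For minors it says: "Parents or guardians will give informed consent on behalf of children who have not reached the age of majority". It then adds: "Children aged from 12 years and age of majority will be required to consent for participation by signing an informed assent form".

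Section 9.2 speaks of the "assent of children over the age of 12 years and 18 years" and says that "their assent should be accompanied by the consent of a parent or guardian".

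Section 6.1, which describes screening and enrolment, has adults consent for themselves and a parent or guardian consent for children. Children from the age of 12 give their assent on top of that.

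The screening form in Appendix 5 has one box for a signed consent form and one for a signed assent form. Its list of inclusion criteria contains no consent item.

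**The concern.** Section 3.5 is the list of conditions a patient must satisfy to enter the study. On its plain wording a parent signs only for a child under 12, and from 12 the patient's own consent suffices. For ages 12 to 17 that is the opposite of what 3.3 and 9.2 require.

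The assent bullet is also faulty. An upper limit of 60 cannot describe minors when majority is 18, and a lower limit of more than 12 leaves out the child who is exactly 12.

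The pregnancy-test bullet adds to the confusion. It uses the under-18 limit that 3.3 implies, but for the test alone. A reader of 3.5 could conclude that the parent of a 15-year-old girl must agree to the test but need not agree to the study.

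What is at stake is participant protection: a minor could be enrolled without the consent that the protocol itself demands elsewhere.

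**Working it through.** There is no figure to reproduce and no formula applies. The check sets the sections side by side by age. Majority is taken as reached at 18, following 3.3 and the pregnancy-test bullet of 3.5.

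| Age | 3.5 | 3.3 | 6.1 | 9.2 |
|---|---|---|---|---|
| Under 12 | Parent or guardian consents | Parent or guardian consents | Parent or guardian consents | Parent or guardian consents |
| Exactly 12 | Patient consents; assent bullet does not apply | Parent consents, child assents | Parent consents, child assents | Parent consents, child assents (wording of the lower limit varies within the section) |
| 13 to 17 | Patient consents; assent as a minor | Parent consents, child assents | Parent consents, child assents (if children means minors) | Parent consents, child assents |
| 18 and over | Patient consents | Patient consents | Patient consents | Patient consents |

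1. Under 12 and from 18 upward, the four sections agree on who consents.
2. From 12 to 17, section 3.5 stands alone in not requiring a parent. Sections 3.3 and 9.2 require one expressly. Section 6.1 does so if its word for children covers everyone below majority, which is the natural reading because it says those from 12 give assent in addition.
3. A child of exactly 12 is not outside section 3.5 altogether. The first bullet covers that child through the patient's own consent. Only the assent bullet misses the age, whereas 3.3 and 6.1 both start assent from 12.
4. The limit of 60 does not impose assent on adults, because the bullet is restricted to minors. It is still wrong as an upper limit for minors.
5. Patients aged 12 to 17 are eligible only for ASP (ages 2 to 60). ASP is given at two of the five sites, Veunsai and Cheu Tom. With 120 patients planned per site, these two enrol 2 × 120 = 240 patients of all ages. The documents do not say what share of them will be 12 to 17, so the number affected cannot be worked out.
6. The Appendix 5 boxes record that a form was signed, not who signed it. By themselves they would not reveal that a parent's consent was missing.

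**The case against.** The strongest reply is that the protocol states the right rule in three other places. Section 9.2 makes consent by the adult patient, or by the parent or guardian of a child, a condition of inclusion in its own right. Section 6.1 is the enrolment procedure itself. Staff who follow either would obtain a parent's consent. The screening form does not carry the under-12 limit, because its inclusion list leaves the consent items out. The consent forms that section 9.2 places in Appendix 10 are not available to this review and may have a parent's signature block with the correct ages.

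Most of this stands. A reader might infer from 3.5 that the protocol permits enrolment of 12- to 17-year-olds without parental consent. Read whole, it does not; that result follows only if 3.5 is applied alone. The need for a new field on the screening form also depends on what the consent form already records.

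A reader might also infer that data from these patients would be lost from site-by-species groups of only 60. The documents do not support that. Such a loss would require an assumed share of 12- to 17-year-olds, that these patients in fact lacked parental consent, and that their data were then removed. Section 3.8 does withdraw patients who fail the inclusion criteria, but a 14-year-old enrolled on his or her own signature would satisfy 3.5 as written.

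The reply does not remove the contradiction. The protocol does not say which section prevails, and the one that is wrong is the eligibility list.

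**Conclusion.** The point holds as a contradiction within the protocol on who must consent for participants aged 12 to 17. Section 3.5 omits the parental consent that 3.3 and 9.2 require, and that 6.1 also asks for. Its assent bullet has an impossible upper limit and misses children of exactly 12.

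The exposure is confined to the two ASP sites; the three ASMQ sites enrol only from 18 and are unaffected. The number of patients cannot be derived from the documents. No effect on sample size, precision or analysis is claimed.

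The conclusion rests on the plain reading of the first 3.5 bullet, in which the under-12 limit governs when a parent signs. The passages should be reconciled before enrolment because the point concerns the protection of minors and the correction is small.

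**What to change.** Amend the two bullets in section 3.5 to agree with 3.3, 6.1 and 9.2:

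- consent from the patient if aged 18 or over, and from a parent or guardian for every participant under 18;
- in addition, assent from every participant aged 12 to under 18.

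Check whether the Appendix 10 consent form identifies the signatory as patient, parent or guardian. If it does not, add a field to the Appendix 5 screening form that records who gave consent.

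This introduces no new standard and changes no treatment, endpoint or sample size. The cost is a minor amendment, which under section 8.4 needs the agreement of the investigator, the sponsor and the review boards, and possibly one reissued form.
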